#### **4.4 Anaphylaxis Study Stopping Rule**

If at any point during the study  $\geq 10\%$  of participants experience an anaphylaxis event, the anaphylaxis study stopping rule will be executed. The study stopping rule will halt any additional enrollment into the study for safety purposes. Additionally, all randomized participants currently receiving study drug will immediately discontinue further study drug administration. The remaining study procedures and visits may be performed if deemed necessary by the Sponsor.

#### **4.5 Temporary Discontinuation of Study Intervention**

Participants may have their study drug administration temporarily suspended during the course of the study. Study drug administration should be temporarily withheld if the participant experiences one or more of the following:

- ALT >3x ULN (moderate)
- Neutrophils <1000/mm^3 (severe)
- Platelet count <50,000/mm^3 (severe)
- Platelet count <75,000/mm^3 (moderate) with evidence of concurrent TIMI major bleeding.

Laboratory measures should be present on two independent assessments. After a temporary suspension of study drug has been performed, study drug may be restarted provided the participant has met the following criteria:

- Neutrophils  $\geq 1500/\text{mm}^3$ , and
- Platelets  $\geq 100,000/\text{mm}^3$

No ongoing clinical sequelae attributable to neutropenia or thrombocytopenia, respectively. If, after restarting study drug, the event causing temporary discontinuation reoccurs study drug should be discontinued permanently.

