### **Laboratory Values**

1. Absolute neutrophil count  $<2.0 \times 10^9/L$  during screening.
2. Platelet count  $<120 \times 10^9/L$  during screening.
3. Spot urine protein to creatinine ratio  $>4000 \text{ mg/g}$ , or  $4.0 \text{ g/g}$ .
4. Alanine aminotransferase (ALT) or aspartate aminotransferase (AST)  $>2.5 \times \text{ULN}$  during screening.
5. Positive testing for tuberculosis (TB) during screening. Blood testing (e.g., QuantiFERON) is preferred but a purified protein derivative (PPD) skin test read within 48-72 hours by a qualified healthcare professional may also be performed. If a patient is PPD positive but QuantiFERON negative the patient is eligible.
6. Evidence of human immunodeficiency virus-1 (HIV-1) or HIV-2 infection by serology measured during screening.
7. Hepatitis B or C by serology (e.g. hepatitis B surface antigen or hepatitis C antibody positive) measured during screening.

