#### **4.3 Criteria for Discontinuation of Study Drug**

It may be necessary for a participant to permanently discontinue study intervention. If study intervention is permanently discontinued, the participant shall remain in the study to be evaluated on all early termination and safety follow-up procedures per the Schedule of Assessments (SOA) in [Section 5.3.9](#) and [Section 5.6](#). Study drug may be prematurely discontinued for a number of reasons, including:

- An intercurrent illness at the discretion of the investigator;
- Any intolerable AE that cannot be ameliorated by appropriate medical intervention or that in the opinion of the Medical Monitor or Investigator would lead to undue risk if the patient were to continue on treatment;
- In the event of severe injection related reactions, anaphylaxis, or hypersensitivity ([Section 8.2](#) and [Section 4.5](#));
- If at any point during the study,  $\geq 10\%$  of subjects enrolled experience anaphylaxis, additional enrollment will stop in the study, and all patients in the study will discontinue receiving study drug ([Section 8.2](#) and [Section 4.4](#));
- Pregnancy;
- Organ transplantation or development of another indication for chronic immunosuppression;

Reasons for all withdrawals/discontinuations of Study Drug will be recorded, and the Medical Monitor should be informed of all such cases as they occur. Temporary discontinuation of study intervention and restarts may be performed per [Section 4.5](#).

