## 9 ADVERSE EVENT REPORTING

### 9.1 Adverse Event Definitions

An AE is any undesirable event or any untoward medical occurrence that occurs to a participant during the course of a study, or the protocol-defined time after study termination, whether or not that event is considered Study Drug-related.

Examples include:

- Any treatment emergent signs and symptoms (events that are marked by a change from the patient's baseline/entry status [e.g., an increase in severity or frequency of pre-existing abnormality or disorder]);
- All reactions from Study Drug, abuse of drug, withdrawal phenomena, sensitivity or toxicity to Study Drug;
- Apparently unrelated illnesses;
- Injuries or accidents (e.g., for a fall secondary to dizziness, record "dizziness" as the event and include the information about the fall in the comment/narrative section and information about any injury secondary to the fall as part of the "outcome");
- Exacerbations (increase in frequency or severity) of symptomatology, subjective patient-reported events, new clinically significant abnormalities in clinical laboratory, physiological testing or physical examination;
- Abnormal laboratory findings considered by the Investigator to be clinically significant. In general, an abnormal laboratory value should not be recorded as an adverse event unless:
  - It is associated with clinical signs or symptoms,
  - Requires an intervention, results in a serious adverse event, or
  - Results in study termination or interruption/discontinuation of study treatment.

However, if none of the above applies, but the laboratory abnormality is considered clinically significantly worsened, it should be reported as a laboratory AE (e.g., "increased white blood cell count"). When recording an adverse event resulting from a laboratory abnormality, the resulting medical condition rather than the abnormality itself should be recorded (e.g., record "anemia" rather than "low hemoglobin").

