## 9.6 Adverse Event Reporting

The AE reporting period starts with randomization and continues through the Week 32 study visit. Patients in this study who experience a drug-related AE or SAE will be followed until the AE or SAE is resolved or stabilizes per the Investigator's judgment, even if this occurs after the final study visit. All AEs spontaneously reported by the patient and/or in response to an open question from study personnel or revealed by observation, physical examination, or other diagnostic procedures will be recorded and reported on the appropriate CRF. When

a unifying diagnosis has been made that accounts for several possible signs and/or symptoms, the unifying diagnosis should be selected as the AE term. For example, the combination of general malaise, mild fever, headache, and rhinitis should be described as “upper respiratory syndrome” if this diagnosis has been made, rather than reporting the individual symptoms as separate events.

If any laboratory test is newly abnormal during the treatment or safety follow-up period, it will be followed at the discretion of the Investigator. Abnormalities of laboratory tests which are, in the opinion of the Investigator, clinically significantly worse compared to baseline, or for which a medical intervention is initiated, should be reported as AEs on the AE CRF.

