#### **13.6 Deviation from the Protocol**

The Investigator will not deviate from the protocol. In medical emergencies, the Investigator will use medical judgment and will remove the patient from immediate hazard, and then notify the Corvidia Therapeutics Medical Monitor and the IRB or IEC immediately regarding the type of emergency and course of action taken. Any action in this regard will be recorded on the appropriate CRF. Any other changes or deviations in the protocol will be made as an amendment to the protocol and must be approved by Corvidia Therapeutics and the IRB or IEC — before the changes or deviations are implemented. Corvidia Therapeutics will not assume any responsibility or liability for any deviation or change.

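### Section 4.5 withholds study drug for ALT above 3x ULN, but its only restart list names neutrophils and platelets and never ALT

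*Protocol*

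**What the plan says.** Section 4.5 (Temporary Discontinuation of Study Intervention) withholds study drug when any one of four findings occurs: "ALT >3x ULN (moderate" grade, as the protocol labels it), neutrophils below 1000/mm3, platelets below 50,000/mm3, or platelets below 75,000/mm3 with TIMI major bleeding. Laboratory findings should be seen on two independent assessments.

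After a suspension, "study drug may be restarted provided the participant has met the following criteria": neutrophils at least 1500/mm3 and platelets at least 100,000/mm3. A further sentence reads "No ongoing clinical sequelae attributable to neutropenia or thrombocytopenia, respectively". The section ends by requiring permanent discontinuation if the event that caused the hold reoccurs after restart.

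Section 4.3 adds no restart level of its own. It refers back: "Temporary discontinuation of study intervention and restarts may be performed per" Section 4.5.

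**The concern.** A hold rule needs an entry condition and an exit condition. For ALT the protocol writes only the first. Because the restart list is worded for any suspension, a site that follows it line by line checks two blood counts that had nothing to do with the hold and finds them satisfied.

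Two decisions depend on the missing level. The first is when to re-dose, where sites may reach different answers for the same ALT course. A dose given too early cannot be taken back, since Section 3.5.4.1 reports a mean terminal half-life of 48 to 56 days in CKD patients. The second is permanent discontinuation. Suppose ALT dips just under 3x ULN, the participant is re-dosed, and ALT then rises just above it. One site may call this a recurrence and stop drug for good; another may call it the same unresolved event and hold again. Nothing in Section 4.5 settles which is right.

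**Working it through.** No sample size, power or alpha figure bears on this point, so the check sets the text side by side.

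**Step 1. Match each trigger in Section 4.5 to its restart level.**

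| Hold trigger | Restart level | Restart level / trigger |
|---|---|---|
| Neutrophils <1000/mm3 | >=1500/mm3 | 1500/1000 = 1.5 |
| Platelets <50,000/mm3 | >=100,000/mm3 | 100,000/50,000 = 2.0 |
| Platelets <75,000/mm3 with TIMI major bleeding | >=100,000/mm3 | 100,000/75,000 = 1.33 |
| ALT >3x ULN | none | none |

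Three of four triggers have a matching level. Of the three restart conditions (neutrophils, platelets, sequelae), none refers to ALT or the liver.

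**Step 2. Look for an ALT restart level elsewhere in the protocol.**

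- Section 4.2, exclusion 4, covers "Alanine aminotransferase (ALT) or aspartate aminotransferase (AST") above 2.5x ULN. This is a screening limit, not a re-dosing rule.
- Section 4.3 sends restarts back to Section 4.5.
- Section 8.1 covers holds for serious infection only. It does give an exit condition (the infection believed fully resolved) and asks for contact with the Medical Monitor about resuming drug. An ALT hold has no counterpart.
- Section 9.1 makes a laboratory abnormality recordable as an adverse event when it "Results in study termination or interruption/discontinuation of study treatment". This governs recording, not dosing.
- Section 9.6 says patients with a drug-related event "will be followed until the AE or SAE is resolved or stabilizes per" the Investigator's judgment. An ALT that is stable but still raised satisfies this.
- Sections 5.3.5, 5.3.7 and 5.3.8 schedule chemistry at the later dosing visits and place dosing after the assessments, but state no ALT value at which dosing may go ahead.

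**Step 3. Apply Section 4.5 to an ALT-only hold with neutrophils >=1500/mm3 and platelets >=100,000/mm3.**

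- *The restart list alone:* all conditions are met on the day the hold begins.
- *The section as a whole:* the trigger still applies while ALT exceeds 3x ULN, and an event can reoccur only after it has ended. This implies restart once ALT is 3x ULN or lower.
- *The list as written for the blood-count holds only,* which the word *respectively* allows: an ALT hold is not addressed and falls to clinical judgment.

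The second reading fits the whole section best, but the reader has to infer it. None of the three gives a stated level for the end of the ALT event.

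**The case against.** The strongest reply is that the hold is a standing instruction. A participant whose ALT is still above 3x ULN still meets it, and a permissive restart clause about blood counts does not cancel it. The recurrence sentence also presumes that the event has ended. This stands. A reader might infer that the protocol allows re-dosing at any ALT value whatever; read as a whole, Section 4.5 does not support that.

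A reader might also set an implied restart at 3x ULN against the 2.5x ULN entry limit and infer added risk. That does not follow either. A participant whose ALT rises on treatment to between 2.5x and 3x ULN is not held, so restarting in that range is consistent with the protocol's own on-treatment rule. Nor does the protocol require a recovery margin for ALT, although it builds one in for the blood counts.

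There are real safeguards. Restart is optional, triggers should be confirmed on two assessments, and under Section 4.3 the Investigator or Medical Monitor can stop drug for undue risk. Section 4.3 also has the Medical Monitor informed of discontinuations of study drug, which may or may not extend to temporary holds. Section 3.6 points to the Investigator's Brochure for monitoring guidance; it is not among the documents and cannot be credited with an ALT level. These safeguards lower the risk. None of them states when an ALT hold ends.

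**Conclusion.** The gap is real and narrow: one of four hold triggers has no stated restart level, and the written list is met at once by an ALT-only hold with adequate counts. The requirement that ALT first return to 3x ULN or below rests on inference and discretion, and the permanent-stop rule lacks a marker for when an ALT event has ended. This is a site dosing rule that the protocol set out to fix and left incomplete; it is not a detail that would normally wait for the SAP.

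It should be corrected, but it is no larger than that. The protocol gives no expected rate of ALT holds, so the number of participants affected is unknown. No endpoint or analysis is shown to be biased, and sample size, power and alpha do not change. The conclusion assumes that no ALT restart level sits in a document not shown, such as the Investigator's Brochure. Even if one did, Section 4.5 would need to refer to it.

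**What to change.** At the next amendment, rewrite the restart list in Section 4.5 so that each condition is tied to its own trigger, and add one for ALT. The sponsor's clinical team should set the level. Examples are ALT no higher than 2.5x ULN, or back to baseline, confirmed before re-dosing and with no ongoing hepatic sequelae. The protocol prescribes neither; 2.5x ULN is simply an ALT limit it already uses. State that drug stays on hold until the condition is met, and that meeting it marks the end of the event for the recurrence rule.

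The cost is procedural. Section 13.6 requires that "changes or deviations in the protocol will be made as an amendment to the protocol and must be approved by Corvidia Therapeutics". Ethics approval is needed as well before the new text is used, here across approximately 50-60 planned sites. A stricter exit condition may delay or lose a few doses. Section 6.1.1 already lets a missed dose be given up to 15 days late, so a hold that clears in that window delays the dose and a longer one forfeits it.

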#### **4.6 Participant Discontinuation/Withdrawal from the Study**

The following are descriptions of participant discontinuation and withdrawal from the study. This is not an exhaustive list, and each instance should be evaluated on a case-by-case basis.

- Withdrawal of consent. A participant may elect to withdraw consent to treatment at any time.
- Participants withdrawing their consent for all study procedures must be given the option to continue to give consent for passive follow-up (i.e., by means of chart review) for AEs.
- Participants discontinuing study drug treatment after receiving any amount of study drug should undergo all early termination and safety follow-up study procedures per the SOA ([Section 5.3.9](#) and [Section 5.6](#)) unless the participant also explicitly withdraws consent for these procedures as mentioned above. The study drug has a long pharmacodynamic effect. Therefore, continued monitoring for pharmacodynamic effects and safety is prudent.

- A participant may be withdrawn at any time at the discretion of the investigator for safety, behavioral, compliance, or administrative reasons. Participation in the early termination and safety follow-up procedures will be evaluated on a case-by-case basis. If possible, participants should take part in the early termination and safety follow-up procedures in the SOA ([Section 5.3.9](#) and [Section 5.6](#)).
- If the participant withdraws consent for disclosure of future information, the sponsor may retain and continue to use any data collected before such a withdrawal of consent.
- If a participant withdraws from the study, the participant may request destruction of any samples taken and not tested. The investigator must document this in the site study records.

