### **11.3.4 Missing Data Handling**

Unless otherwise specified, missing data will not be imputed and the analyses will be based on observed data only.

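### Section 4.6 makes safety follow-up discretionary after investigator-initiated withdrawal, at odds with Section 4.3, so later harm data can be lost selectively by arm

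*Protocol*

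**What the plan says.** Section 4.3 covers permanent discontinuation of study drug. Its listed reasons include an intolerable adverse event and an event that the Medical Monitor or investigator judges to carry undue risk. Its rule is firm: "If study intervention is permanently discontinued, the participant shall remain in the study to be evaluated on all early termination and safety follow-up procedures".

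The third bullet of Section 4.6 gives the same direction for patients who stop drug, excepting only those who explicitly withdraw consent for the procedures. It gives a reason: "The study drug has a long pharmacodynamic effect". The fourth bullet then introduces a different route: "A participant may be withdrawn at any time at the discretion of the investigator for safety, behavioral, compliance, or administrative reasons". For these patients the protocol says "Participation in the early termination and safety follow-up procedures will be evaluated on a case-by-case basis", and adds: "If possible, participants should take part in the early termination and safety follow-up procedures in the SOA".

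Other sections bear on the point:
- Section 5.6 asks for an early termination visit from any randomized patient leaving before Week 24 (Week 24 procedures) or between Weeks 24 and 32 (Week 32 procedures).
- Section 8.2 keeps patients with severe injection reactions, anaphylaxis or hypersensitivity in follow-up, off drug.
- Section 9.6: "The AE reporting period starts with randomization and continues through the Week 32 study visit". It also follows drug-related events until they resolve or stabilize.
- Section 11.3.4 provides that, unless otherwise specified, "missing data will not be imputed and the analyses will be based on observed data only".

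**The concern.** A patient with a worrying adverse event can be handled under either of two rules. If the investigator stops the drug, follow-up is required. If the investigator instead withdraws the patient from the study for safety, the same follow-up becomes a matter of judgement, although the patient has not refused it. The protocol does not say what separates the two cases.

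Investigator withdrawals for safety may well differ between dose groups. If they do, harm data after withdrawal would be missing unequally across arms, and no analysis plan can recover observations that were never collected. This matters because Section 2 ties the choice of dose to an hs-CRP reduction with acceptable LDL-C or triglyceride increases and without meaningful falls in neutrophils and platelets. Each arm has only 60 patients, and Sections 12.1 and 12.2 provide neither an events committee nor a safety assessment committee.

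**Working it through.** **1. The rules side by side, for a patient who has not withdrawn consent**

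| Situation | Section | Early termination and safety follow-up |
|---|---|---|
| Drug stopped for an intolerable event or undue risk | 4.3 | Required |
| Drug stopped after any dosing | 4.6, third bullet | Expected unless consent is withdrawn |
| Severe reaction | 8.2 | Patient stays in follow-up |
| Leaves the study early | 5.6 | Early termination visit expected |
| Withdrawn by the investigator, including for safety | 4.6, fourth bullet | Case by case, then if possible |

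The last row stands apart. There is also an imbalance inside Section 4.6. A patient who withdraws consent for all procedures must be offered passive adverse-event follow-up. A patient removed by the investigator has no such guarantee.

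**2. What the other sections secure**

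The Section 5.6 visit before Week 24 is a single visit and does not replace the Week 28 and Week 32 safety visits. Section 9.6 follows drug-related events already known; it does not secure detection of new events, or follow-up of events judged unrelated. Section 11.4.5.1 tabulates treatment-emergent events leading to discontinuation of the study, so the triggering event is counted. What remains exposed is new or later events and later laboratory values.

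**3. How long the exposed period can be**

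Inputs: the Week 5 visit opens on Day 29 and the Week 32 visit on Day 218 (Table 2); mean terminal half-life in CKD patients is 48 to 56 days (Section 3.5.4.1).
- A patient withdrawn just after the second dose can lose up to 218 − 29 = 189 days (27 weeks) of adverse-event collection. This is an upper bound.
- Fraction remaining 28 days later, by elimination alone: 2^(−28/48) = 0.667 to 2^(−28/56) = 0.707. Much of this period is therefore time with drug on board, which agrees with the reason given in Section 4.6 for continued monitoring.

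**4. Primary endpoint**

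Inputs from Section 11.1: difference 60.74 points, SD 16.893, 54 per group, two-sided alpha 0.05, 10% dropout.
- Noncentrality = 60.74 / (16.893 × √(2/54)) = 18.68, giving power of 1.000 to three decimals. This reproduces the stated figure of more than 99%.
- 54 / (1 − 0.10) = 60 per group, as planned.
- With only 30 evaluable per group, power on these inputs is still 1.000.
- Shift in an arm mean = fraction lost × difference between lost and retained patients. Under assumed values of 2% to 10% lost and a 25 to 100 point difference, this runs from 0.02 × 25 = 0.5 to 0.10 × 100 = 10 points, against 60.74.

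The issue is therefore ascertainment of harm, not power.

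**5. Scale of the harm under-count**

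The only figure in the protocol is all-cause dropout: 10% of 240 = 24 patients, or 6 per arm. It does not give the share withdrawn by investigators for safety, or their later event risk. As an illustration with assumed inputs only, suppose 4 of 60 are withdrawn for safety at one dose and 1 of 60 on placebo, each with a 15% to 30% later risk of a serious event, and that every such event goes unseen. Unseen events are then 4 × 0.15 to 4 × 0.30 = 0.6 to 1.2, against 0.15 to 0.30. The difference is 0.45 to 0.90 events, and dividing by 60 gives 0.75 to 1.5 percentage points. This shows order of magnitude and is not an estimate.

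**The case against.** The best reply is that the two rules address different events: Section 4.3 deals with stopping drug and the fourth bullet of 4.6 with leaving the study. Most foreseeable safety problems are also routed to continued follow-up. Recurrent low neutrophil or platelet counts after a restart lead under Section 4.5 to permanent drug discontinuation, and so to 4.3; severe reactions fall under 8.2; intolerable events and undue risk are named in 4.3 itself. The fourth bullet is then residual, and it states an expectation of follow-up where possible.

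The distinction between stopping drug and leaving the study is correct, but it locates the gap without closing it. The bullet names safety as a reason for withdrawal, and nothing confines it to cases that 4.3 does not cover.

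The reply does defeat some stronger readings that a reader might infer:
- *That outcomes are lost, and in exactly the patients with safety problems.* The text supports only that they can be lost. The bullet also covers behavioral, compliance and administrative reasons.
- *That a harmful dose will necessarily look safer.* The triggering event is tabulated in its arm and known drug-related events are followed. Only further or later findings are exposed, and any imbalance between arms is a possibility, not a stated fact.
- *That the primary result is compromised.* The repeated-measures model in Section 11.4.3 uses each patient's observed values, and sensitivity analyses for the primary endpoint are promised.
- *That aligning 4.6 with 4.3 would restore Week 13 hs-CRP.* Section 4.3 secures early termination and safety follow-up procedures, not the scheduled Week 13 visit for patients who stop before it.

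**Conclusion.** The inconsistency is real and should be corrected. For a patient with an investigator-judged safety problem and intact consent, Section 4.3 requires early termination and safety follow-up, while the fourth bullet of Section 4.6 allows the investigator to end participation and leaves those procedures to discretion. New or later adverse events and neutrophil, platelet and lipid values can be lost as a result, possibly unevenly by arm.

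The effect on power for hs-CRP is negligible under the protocol's own inputs. The size of any harm under-count cannot be derived from the document. The conclusion rests on the wording of the rules and on the possibility, not shown in the protocol, that safety withdrawals by investigators differ between arms.

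**What to change.** Reconcile Sections 4.3, 4.6 and 5.6 by separating two decisions: stopping study drug and ending data collection. In the fourth bullet of 4.6, replace the case-by-case sentence with a default. After investigator-initiated withdrawal, the early termination visit and the scheduled safety and adverse-event follow-up through Week 32 take place unless the participant withdraws consent, dies or is lost to follow-up, or the sponsor ends the study. Offer passive adverse-event follow-up where visits cannot be done, and record the reason whenever procedures are missed. While doing so, align the end of passive follow-up, given as Week 21 in Section 5.6, with the Week 32 end of the reporting period in Section 9.6.

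This does not alter who stops drug or when. The cost is an amended bullet with matching wording in 5.6, plus a few visits already in the schedule kept for a few more patients.
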